- ^d Includes hFVIII activity level (one-stage clotting and chromogenic substrate assay), Bethesda assay (with Nijmegen modification) for hFVIII inhibitor level, hFVIII coagulation activity exploratory assay, and hFVIII antigen (ELISA). If a subject has used FVIII within 72 hours of a measurement day, all efforts should be made to obtain FVIII activity measurements when a 72 hour interval without FVIII use is achieved; the 72-hour wash-out period is only intended for subjects who have achieved FVIII ≥ 5 IU/dL at 16 weeks after BMN 270 infusion and who have not resumed standard of care FVIII replacement therapy. If FVIII levels are elevated or stable over the course of several weeks, assessment of FVIII activity may be adjusted based on discussion between the Medical Monitor and the Investigator. A d-dimer may be considered under circumstances in which FVIII activity levels are above the normal physiological range and/or if there is a concern for a venous thromboembolism. ^e Sample testing during Safety Follow-Up is not required if at least 3 consecutive samples are cleared during the Post-Infusion Follow-Up period.
- ^f Blood samples will be collected to evaluate biochemical, molecular, cellular, and genetic/genomic aspects relevant to hemophilia A, coagulation, and/or AAV gene transfer, and to develop assays used for these evaluations. Subjects may choose to opt out of the exploratory genetic/genomic research being done to study or try to discover genes that are not yet known to be associated with hemophilia A. While exploratory samples will be collected at the time points indicated above, testing of these samples (including those for Direct Thrombin Activity test and any other exploratory assessments) will be performed only as deemed necessary by the Sponsor.

Table 9.1.5: Schedule of Events – Safety Follow-Up (Years 2-7)

	Years 2-5*	Year 2*	Years 3-5*	Years	6-7]	End of Y	ear Visit	s		
				Q13W		Year 2	Year 3	Year 4	Year 5	Year 6	Year 7	
Assessment	Q12W	Q4W ^h	Q6W ^{h,j}	(Remote) ⁱ	Q26W	W104	W156		W260	W312	W364	ETV
Physical examination ^a	Xa							Ka		X	X	X
Weight ^a	Xa						У	Ka		X	X	X
Assessment of Adverse Events and Concomitant Medications (including review of subject diary for bleeding and FVIII use)	X	Х	Х	Х	Х		Σ	X		Х	Х	Х
Vital Signs	X						2	X		X	X	X
Blood chemistry, haematology, coagulation screen, and CRP ^b	X				X		2	K		Х	X	X
Urine Tests ^b	X						2	X				X
Liver Tests (local) ^b	X	Х	X				2	X				Х
FVIII assays (local) ^c	X	X	X				2	X				X
Liver Tests (central) ^b	X	X	X		X		2	X		Х	Х	X
FVIII assays (central) ^d	X	X	X		X		2	X		X	X	Х
FVIII Antigen assay	X				X		Σ	K		X	Х	Х
AAV5 antibody titer							2	K		Х	Х	Х
FVIII antibody titer							2	K		X	X	X
PBMC Collection (for determination of FVIII and Capsid specific CTL activity)	X						Σ	K				X
Von Willebrand Factor Antigen (VWF:Ag)	Х						Σ	K				Х
PCR of vector DNA in semen ^e	Xe	Xe	Xe		Xe		У	Ke		Xe	Xe	Х
PRC of vector DNA in blood, saliva, urine, stools ^e	Xe				Xe		У	Ke		Xe	Xe	Х
Exploratory biomarker assessments ^g	Х						2	X		Х	Х	Х

Proprietary and Confidential

24 August 2021

270-201 Amendment 10

Page 50

	Years 2-5*	Year 2*	Years 3-5*	Years	6-7		1	End of Y	ear Visit	5	-	
				Q13W		Year 2	Year 3	Year 4	Year 5	Year 6	Year 7	
Assessment	Q12W	Q4W ^h	Q6W ^{h,j}	(Remote) ⁱ	Q26W	W104	W156	W208	W260	W312	W364	ETV
Haemo-QoL-A QoL assessment	Xf				\mathbf{X}^{f}		Х	Kf		\mathbf{X}^{f}	Xf	X
Liver ultrasound ^k							X ^k (Yea	r 5 only)		X^k	X^k	Х

ETV: Early Termination Visit

* Visit windows are ± 2 weeks for visits in Years 2-5 and ± 4 weeks for visits in Years 6-7. The Q6W visits during Years 3-5 should restart after each End of Year visit (eg, the first Q6W visit during Year 3 should be ~6 weeks after the End of Year 2 visit).

^a Complete physical examination should be performed at the End of Year visits (genitourinary examination may be deferred unless the subject has genitourinary-related complaints); brief physical examination may be performed at other study visits. Weight should be recorded at the second Q12W visit each year during Years 2-5, and at every End of Year visit during Years 2-7.

- ^b Refer to Table 9.7.9.2.1 for laboratory assessments to be included, and to Table 9.7.9.3.1 for liver tests. LTs may be assessed more frequently when ALT values are $\geq 1.5x$ ULN or based upon discussion between the Medical Monitor and the Investigator. Subjects with ALT $\geq 1.5x$ ULN during the study may undergo additional evaluations (eg, imaging studies including MRI or ultrasound, additional blood tests, and/or liver biopsy) at the discretion of the investigator. Additional testing of FVIII and LTs during any study week may be performed if: (1) the ALT has increased to above ULN or increased by ≥ 10 U/L from prior assessment;; or (2) after a discussion between the Medical Monitor and the Investigator based on a review of subject data. If ALT values are stable over the course of several weeks, assessment of FVIII activity and ALT levels may be adjusted based on discussion between the Medical Monitor and the Investigator. During Years 2-5 of the Post-Infusion Follow-Up period, urine tests and blood, chemistry, and coagulation tests should be performed at the second Q12W visit each year and at every End of Year visit. During Years 6-7, these tests should be performed at the Q26W and End of Year visits.
- ^c Includes hFVIII activity level (one-stage clotting and chromogenic substrate assay). If a subject has used FVIII within 72 hours of a measurement day, all efforts should be made to obtain FVIII activity measurements when a 72 hour interval without FVIII use is achieved; the 72-hour wash-out period is only intended for subjects who have achieved FVIII \geq 5 IU/dL at 16 weeks after BMN 270 infusion and who have not resumed standard of care FVIII replacement therapy. If FVIII levels are elevated or stable over the course of several weeks, assessment of FVIII activity may be adjusted based on discussion between the Medical Monitor and the Investigator. A d-dimer may be considered under circumstances in which FVIII activity levels are above the normal physiological range and/or if there is a concern for a venous thromboembolism. If a subject tests positive in the Bethesda assay (with Nijmegen modification) during Years 3-5, a fresh sample should be collected within 4 weeks of the initial visit that had a positive result.

^d Includes hFVIII activity level (one-stage clotting and chromogenic substrate assay), Bethesda assay (with Nijmegen modification) for hFVIII inhibitor level, and hFVIII coagulation activity exploratory assay. If a subject has used FVIII within 72 hours of a measurement day, all efforts should be made to obtain FVIII activity

Proprietary and Confidential

24 August 2021

BOMARIN Page 51 270-201 Amendment 10

measurements when a 72 hour interval without FVIII use is achieved; the 72-hour wash-out period is only intended for subjects who have achieved FVIII \geq 5 IU/dL at 16 weeks after BMN 270 infusion and who have not resumed standard of care FVIII replacement therapy. If FVIII levels are elevated or stable over the course of several weeks, assessment of FVIII activity may be adjusted based on discussion between the Medical Monitor and the Investigator. A d-dimer may be considered under circumstances in which FVIII activity levels are above the normal physiological range and/or if there is a concern for a venous thromboembolism. If a subject tests positive in the Bethesda assay (with Nijmegen modification) in Years 3-5, a fresh sample should be collected within 4 weeks of the initial visit that had a positive result.

- ^e Sample testing during Safety Follow-Up is not required if at least 3 consecutive samples are cleared during the Post-Infusion Follow-Up period. Subjects who have not had 3 consecutive negative semen samples by Week 52 should continue to have PCR testing every 4 weeks (during Year 2), every 6 weeks (during Years 3-5), and/or every 26 weeks (during Years 6-7) until 3 consecutive samples below the limit of detection are documented (or upon consultation between the Investigator and Medical Monitor).
- ^fHaemo-QoL-A QoL assessment during Years 2-5 of Safety Follow-up should be performed at the second Q12W visit each year and at every End of Year visit. During Years 6-7, the Haemo-QoL-A assessment should be performed at the Q26W visits and the End of Year visits.
- ^g Blood samples will be collected to evaluate biochemical, molecular, cellular, and genetic/genomic aspects relevant to hemophilia A, coagulation, and/or AAV gene transfer, and to develop assays used for these evaluations. Subjects may choose to opt out of the exploratory genetic/genomic research being done to study or try to discover genes that are not yet known to be associated with hemophilia A. While exploratory samples will be collected at the time points indicated above, testing of these samples (including any other exploratory assessments) will be performed only as deemed necessary by the Sponsor.
- ^h Subjects who meet the definition of treatment failure to BMN 270 therapy after Week 52 may omit the Q4W and Q6W visits during Years 2-5, and must attend only the Q12W and End of Year visits. Such subjects following the abbreviated schedule who have not yet cleared vector shedding in semen must still provide samples Q4W (during Year 2), Q6W (during Years 3-5), or Q26W (during Years 6-7), until vector shedding has been cleared (but do not need to do other scheduled assessments at those visit dates), either by reporting to the site to provide samples or by providing those samples to an MN professional.
- ¹ For every 13 week remote visits during Years 6-7, the site should contact the subject to collect data on adverse events, new or changed concomitant medications, and diary entries (FVIII usage and bleeding events).
- ^j At applicable sites, certain study assessments designated in the Schedule of Events may be performed by a mobile nursing (MN) professional at the subject's home or another suitable location, such as their school or office. Refer to Section 9.7.9.2 for details.
- ^k Additional liver ultrasounds may be performed at interim timepoints (ie, between the End of Year visits) at the discretion of the Investigator.

Table 9.1.6: Schedule of Events – Reactive Corticosteroids for LT Elevations

	Steroid Treatment Period ^d									Post-Steroid Period ^c						
	Week 1	Week 2	Week 3	Week 4	Week 5	Week 6	Week 7	Week 8	Week 9	Week 10	Week 11 ^b	Week 1	Week 2	Week 3	Week 4	Week 13
Reactive corticosteroids (dose in mg/day) ^a	60 mg	60 mg	40 mg	40 mg	30 mg	30 mg	20 mg	20 mg	15 mg	10 mg	5 mg					
FVIII activity testing												Х	X	Х	Х	
Liver testing												Х	X	X	Х	
Hepatitis B testing ^e						Х						Х				X
HCV Viral Load ^e						Х						Х				Х

^a Reactive corticosteroids may be initiated when a subject's ALT value is \geq 1.5x ULN or based on review of FVIII and liver enzyme data after consultation between the Investigator and the Medical Monitor.

^b Following initiation or completion of steroid regimen, if ALT elevation $\geq 1.5x$ ULN is reported, steroid management decisions will based on discussions between the Investigator and Medical Monitor. Modification of the steroid regimen may take into consideration timing of the ALT elevation (after Week 52), as well as possible confounders for the ALT elevation and adverse events related to corticosteroid dosing. Guidance for tapering oral corticosteroids can be found in Section 9.4.8.2.

^c After discontinuation of corticosteroids, weekly labs for ALT and FVIII levels will be measured once a week for 4 weeks to ensure stability in values. If these assessments are already being done as part of normal study follow-up, they do not need to be duplicated.

^d Regardless of the assessments listed in the Schedule of Assessments (Table 9.1.2, Table 9.1.3, or Table 9.1.4), subjects initiated on corticosteroids will only be required to have laboratory evaluations on a weekly basis.

^e Should only be performed in subjects with a history of hepatitis B or hepatitis C prior to study entry.

270-201 Amendment 10

Table 9.1.7: Schedule of Events – Liver Biopsy Substudy

	Within 28 Days Before Biopsy Day	Within 7 Days Before Biopsy Day	1 Day Before Biopsy Day ^d	Biopsy Day (BD)
Informed Consent	X			
Liver Ultrasound ^a	X			
Brief Physical Examination	X		X	Х
Hematology, Coagulation, Chemistry Assessments ^b	X		X	
Liver Tests ^b	X		X	Х
FibroScan		Х		
Local FVIII Activity Level Assessment		Х	X	Х
Pre-Biopsy Consultation ^c		Х		
Liver Biopsy ^e				Х

^a Liver ultrasound must be performed within 28 days prior to the scheduled biopsy, unless an ultrasound result from the prior 3 months is already available.

^b Refer to Table 9.7.9.2.1 for laboratory assessments to be included, and to Table 9.7.9.3.1 for liver tests.

^c Subjects will undergo a pre-biopsy consultation with the investigator (treating hematologist).

^d Subjects may need to repeat/extend this visit if their FVIII activity levels need adjustment before the biopsy, at the discretion of the investigator (treating hematologist).

^e Biopsy will be a percutaneous or transjugular biopsy under ultrasound guidance, performed according to the standard procedure of the institution. If only a small amount of tissue (< 2 cm) is obtained at the time of the biopsy, the subject may be asked to consent for a second pass. In this case, the original < 2 cm sample should still be retained and handled according to the instructions for handling biopsy specimens in the Laboratory Manual. Following completion of the biopsy, the subject should remain in the hospital under observation for at least 4-6 hours. Overnight post-procedure observation may be done at the investigator's discretion.

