^d Includes hFVIII activity level (one-stage clotting assay and chromogenic substrate assay), Bethesda assay (with Nijmegen modification) for hFVIII inhibitor level, hFVIII coagulation activity exploratory assay, and hFVIII antigen (ELISA). If a subject has used FVIII within 72 hours of a measurement day, all efforts should be made to obtain FVIII activity measurements when a 72-hour interval without FVIII use is achieved; the 72-hour wash-out period is only intended for subjects who have achieved FVIII \geq 5 IU/dL at 16 weeks after BMN 270 infusion and who have not resumed standard of care FVIII replacement therapy. If FVIII levels are elevated or stable over the course of several weeks, assessment of FVIII activity may be adjusted based on discussion between the Medical Monitor and the Investigator. A d-dimer may be considered under circumstances in which FVIII activity levels are above the normal physiological range and/or if there is a concern for a venous thromboembolism.

^e Collection to occur on Day 2 and 4 following BMN 270 infusion, and then until at least 3 consecutive negative results are obtained. Collection and testing of semen samples must continue through Week 12, even if 3 consecutive negative samples in that compartment have already been recorded.

- ^f Blood samples will be collected to evaluate biochemical, molecular, cellular, and genetic/genomic aspects relevant to hemophilia A, coagulation, and/or AAV gene transfer, and to develop assays used for these evaluations. Subjects may choose to opt out of the exploratory genetic/genomic research being done to study or try to discover genes that are not yet known to be associated with hemophilia A. While exploratory samples will be collected at the time points indicated above, testing of these samples (including those for Direct Thrombin Activity test and any other exploratory assessments) will be performed only as deemed necessary by the Sponsor.
- ^g Testing for reactivation of hepatitis B and hepatitis C at Week 16, for subjects with a past medical history of Hepatitis B or Hepatitis C prior to study entry, should be performed only in subjects who have not received reactive corticosteroids prior to Week 16; subjects who have received reactive corticosteroids will have hepatitis B and hepatitis C testing at the time points indicated in Table 9.1.6.

Proprietary and Confidential

24 August 2021

270-201 Amendment 10

Table 9.1.3: Schedule of Events – Safety Follow-Up (Week 17-32)

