12.5.4 Every 2 Weeks

Every 2 weeks (Weeks 2, 4, 6, 8, 10, 12, 14 and 16), the following procedures will be performed:

- Blood chemistry, haematology, coagulation screen, and CRP (refer to Table 9.7.9.2.1) (not assessed at Week 14)
- PCR of vector DNA in blood, saliva, urine, semen, and stools (not collected at Week 2)
 - Collection to occur until at least 3 consecutive negative results are obtained. Semen samples should continue to be collected and tested through Week 12, even if 3 consecutive negative results in that compartment have been recorded prior to that timepoint.

12.5.5 Weeks 4, 8, 12, and 16

At Weeks 4, 8, 12, and 16, the following procedures will be performed:

- Urine Tests (refer to Table 9.7.9.2.1)
- VWF:Ag
- FVIII antibody titer
- Exploratory biomarker assessments

12.5.6 Week 16

At Week 16, the following procedures will be performed:

- Test for hepatitis B and hepatitis C reactivation (in subjects with a history of hepatitis B or hepatitis C infection prior to study entry)
 - Subjects who receive reactive corticosteroids prior to Week 16 do not need to complete the Week 16 reactivation assessment; instead, they will be tested for hepatitis B and hepatitis C reactivation at the time points listed in Table 9.1.6.

12.5.7 Weeks 8 and 16

At Weeks 8 and 16, the following procedures will be performed:

• AAV5 antibody titer

12.5.8 Weeks 2, 3, 4, and 16

At Weeks 2, 3, 4, and 16, the following procedure will be performed:

• Haemo-QoL-A QoL assessment

12.5.9 Week 13

At Week 13, the following procedure will be performed:

• Direct Thrombin test

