12.8.1 Year 2 – Every 4 Weeks (not required for treatment failure)

During Year 2, every 4 weeks (\pm 2 weeks), the following procedures will be performed:

- Assessment of Adverse Events and Concomitant Medications (including review of subject diary for bleeding and FVIII use)
- Liver Tests (refer to Table 9.7.9.3.1) local laboratory assessment
 - LTs may be monitored more or less frequently (and in particular when ALT values are >1.5x ULN) based on discussion between the Medical Monitor and the Investigator and review of subject data.
- FVIII activity level local laboratory assessment
 - FVIII activity level (one-stage clotting assay)
 - FVIII activity level (chromogenic substrate assay)
- Liver Tests (refer to Table 9.7.9.3.1) central laboratory assessment
 - LTs may be monitored more or less frequently (and in particular when ALT values are >1.5x ULN) based on discussion between the Medical Monitor and the Investigator and review of subject data.

- FVIII Assays central laboratory assessment
 - FVIII activity level (one-stage clotting assay)
 - FVIII activity level (chromogenic substrate assay)
 - o FVIII coagulation activity exploratory assay
 - o Bethesda assay (with Nijmegen modification) for FVIII inhibitor level
 - FVIII antigen (ELISA)

Note: If a subject has used FVIII within 72 hours of a measurement day, all efforts should be made to obtain FVIII activity measurements when a 72-hour interval without FVIII use is achieved; the 72-hour wash-out period is only intended for subjects who have achieved FVIII \geq 5 IU/dL at 16 weeks after BMN 270 infusion and who have not resumed standard of care FVIII replacement therapy.

- PCR of vector DNA in blood, saliva, urine, semen, and stools (if required)
 - Sample testing during Year 2 is not required if at least 3 consecutive samples are negative during the Post-Infusion Follow-Up period in Weeks 1-52.
 Subjects who have not had 3 consecutive negative semen samples by Week 52 should continue to have PCR testing of semen every 4 weeks during Year 2 until 3 consecutive negative samples are documented (or upon consultation between the Investigator and Medical Monitor).

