12.8.2 Years 3-5 – Every 6 Weeks (not required for treatment failure)

During Years 3-5, every 6 weeks (± 2 weeks), the following procedures will be performed:

- Assessment of Adverse Events and Concomitant Medications (including review of subject diary for bleeding and FVIII use)
- Liver Tests (refer to Table 9.7.9.3.1) local laboratory assessment
 - LTs may be assessed more frequently when ALT values are >1.5x ULN or based upon discussion between the Medical Monitor and the Investigator and review of subject data.
- FVIII activity level local laboratory assessment
 - FVIII activity level (one-stage clotting assay)
 - FVIII activity level (chromogenic substrate assay)

- Liver Tests (refer to Table 9.7.9.3.1) central laboratory assessment
 - LTs may be assessed more frequently when ALT values are >1.5x ULN or based upon discussion between the Medical Monitor and the Investigator and review of subject data.
- FVIII Assays central laboratory assessment
 - FVIII activity level (one-stage clotting assay)
 - FVIII activity level (chromogenic substrate assay)
 - o FVIII coagulation activity exploratory assay
 - o Bethesda assay (with Nijmegen modification) for FVIII inhibitor level

Note: If a subject has used FVIII within 72 hours of a measurement day, all efforts should be made to obtain FVIII activity measurements when a 72-hour interval without FVIII use is achieved; the 72-hour wash-out period is only intended for subjects who have achieved FVIII \geq 5 IU/dL at 16 weeks after BMN 270 infusion and who have not resumed standard of care FVIII replacement therapy.

- PCR of vector DNA in blood, saliva, urine, semen, and stools (if required)
 - Sample testing during Years 3-5 is not required if at least 3 consecutive samples are negative during the Post-Infusion Follow-Up period in Weeks 1-52 and/or Year 2. Subjects who have not had 3 consecutive negative semen samples by the end of Year 2 should continue to have PCR testing of semen every 6 weeks during Years 3-5 until 3 consecutive samples below the limit of detection are documented (or upon consultation between the Investigator and Medical Monitor).

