Note: If a subject has used FVIII within 72 hours of a measurement day, all efforts should be made to obtain FVIII activity measurements when a 72-hour interval without FVIII use is achieved; the 72-hour wash-out period is only intended for subjects who have achieved FVIII \geq 5 IU/dL at 16 weeks after BMN 270 infusion and who have not resumed standard of care FVIII replacement therapy.

• Vital Signs

- Blood chemistry, haematology, coagulation screen, and CRP (refer to Table 9.7.9.2.1)
 - ABO blood typing assessment should be performed at the next regularly scheduled study visit (or at least prior to the end of the subject's participation in the study)
- Urine Tests (refer to Table 9.7.9.2.1)
- FVIII antigen (ELISA)
- AAV5 antibody titer (at End of Year visits only)
- FVIII antibody titer (at End of Year visits only)
- PBMC collection
- VWF:Ag
- Exploratory biomarker assessments
- Haemo-QoL-A QOL assessment (at Week 76, Week 128, Week 180, Week 232, and End of Year visits only)
- Liver ultrasound (at End of Year 5 visit only)
 - Additional liver ultrasounds may be performed at interim time points (ie, between the End of Year visits) at the discretion of the Investigator.
- PCR of vector DNA in blood, saliva, urine, semen, and stools (if required)
 - Sample testing during Years 2-5 is not required if at least 3 consecutive samples are negative during the Post-Infusion Follow-Up period in Weeks 1-52. Subjects who have not had 3 consecutive negative semen samples by Week 52 should continue to have PCR testing of semen every 4 weeks (during Year 2) or every 6 weeks (during Years 3-5) until 3 consecutive samples below the limit of detection are documented (or upon consultation between the Investigator and Medical Monitor).

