12.9.2 Years 6-7 – Every 26 Weeks and End of Year Visits

During Years 6-7, the following assessments will be performed at a site visit every 26 weeks $(\pm 4 \text{ weeks})$ (Week 286 and Week 338) and at the End of Year Visits $(\pm 4 \text{ weeks})$ (Week 312 and Week 364):

- Assessment of Adverse Events and Concomitant Medications (including review of subject diary for bleeding and FVIII use)
- Complete Physical Examination (genitourinary examination may be deferred unless the subject has genitourinary-related complaints) (Week 312 and Week 364 only)
- Weight (Week 312 and Week 364 only)
- Vital signs (Week 312 and Week 364 only)
- Blood chemistry, haematology, coagulation screen, and CRP (refer to Table 9.7.9.2.1)
- Liver Tests (refer to Table 9.7.9.3.1) central laboratory assessment
 - LTs may be assessed more frequently when ALT values are >1.5x ULN or based upon discussion between the Medical Monitor and the Investigator and review of subject data.
- FVIII Assays central laboratory assessment
 - FVIII activity level (one-stage clotting assay)
 - FVIII activity level (chromogenic substrate assay)
 - FVIII coagulation activity exploratory assay
 - Bethesda assay (with Nijmegen modification) for FVIII inhibitor level

Note: If a subject has used FVIII within 72 hours of a measurement day, all efforts should be made to obtain FVIII activity measurements when a 72-hour interval without FVIII use is achieved; the 72-hour wash-out period is only intended for subjects who have achieved FVIII \geq 5 IU/dL at 16 weeks after BMN 270 infusion and who have not resumed standard of care FVIII replacement therapy.

- FVIII antigen (ELISA)
- AAV5 antibody titer (Week 312 and Week 364 only)
- FVIII antibody titer (Week 312 and Week 364 only)
- Exploratory biomarker assessments (Week 312 and Week 364 only)
- Haemo-QoL-A QOL assessment

Proprietary and Confidential

- Liver ultrasound (Week 312 and Week 364 only)
 - Additional liver ultrasounds may be performed at interim time points at the discretion of the Investigator.
- PCR of vector DNA in blood, saliva, urine, semen, and stools (if required)
 - Sample testing during Years 6-7 is not required if at least 3 consecutive samples are below the limit of detection as of the end of Year 5.

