12.11 Early Termination Visit

The Early Termination visit will occur on the date the subject withdraws from the study, even if the date does not correspond to a protocol-specific visit.

BIOMARIN[®] 270-201 Amendment 10

If a subject leaves the study prior to the Week 364 visit, the subject will be asked to return to the study site and complete an Early Termination visit. At the Early Termination visit, as many of the following assessments as possible should be done:

- Physical examination
- Assessment of Adverse Events and Concomitant Medications (including review of subject diary for bleeding and FVIII use)
- Vital Signs
- Blood chemistry, haematology, coagulation screen, and CRP (refer to Table 9.7.9.2.1)
- Urine Tests (refer to Table 9.7.9.2.1)
- Liver Tests (refer to Table 9.7.9.3.1) local laboratory assessment
- FVIII activity level local laboratory assessment
 - FVIII activity level (one-stage clotting assay)
 - FVIII activity level (chromogenic substrate assay)
- Liver Tests (refer to Table 9.7.9.3.1) central laboratory assessment
- FVIII Assays central laboratory assessment
 - FVIII activity level (one-stage clotting assay)
 - FVIII activity level (chromogenic substrate assay)
 - o FVIII coagulation activity exploratory assay
 - Bethesda assay (with Nijmegen modification) for FVIII inhibitor level

Note: If a subject has used FVIII within 72 hours of a measurement day, all efforts should be made to obtain FVIII activity measurements when a 72-hour interval without FVIII use is achieved; the 72-hour wash-out period is only intended for subjects who have achieved FVIII \geq 5 IU/dL at 16 weeks after BMN 270 infusion and who have not resumed standard of care FVIII replacement therapy.

- FVIII antigen (ELISA)
- AAV5 antibody titer
- FVIII antibody titer
- PBMC collection
- VWF:Ag

- Liver ultrasound
- PCR of vector DNA in blood, saliva, urine, semen, and stools
 - Sample testing at the ETV is not required if at least 3 consecutive samples are below the limit of detection prior to the ETV.
- Exploratory biomarker assessment
- Haemo-QoL-A QOL assessment

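### Semen vector-DNA testing is waived by any past run of three negatives, so the waivers end required testing even in a man whose latest sample is detectable

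*Protocol*

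**What the plan says.** All references are to Protocol Amendment 10.

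**Duty to keep testing early.** Semen is sampled on Days 2, 4 and 8, every two weeks from Week 4 to Week 16, then every four weeks to Week 52, until three consecutive negatives are obtained. Table 9.1.2 footnote e adds a floor: "Collection and testing of semen samples must continue through Week 12, even if 3 consecutive negative samples in that compartment have already been recorded". Sections 9.7.9.7 and 12.5.4 repeat it.

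**Waivers of later testing.**
- Table 9.1.4 footnote e and Table 9.1.5 footnote e: "Sample testing during Safety Follow-Up is not required if at least 3 consecutive samples are cleared during the Post-Infusion Follow-Up period". Sections 12.6.4 and 12.7.2 say the same in slightly different words.
- Section 12.8.1: "Sample testing during Year 2 is not required if at least 3 consecutive samples are negative during the Post-Infusion Follow-Up period in Weeks 1-52".
- Section 12.8.2: "not required if at least 3 consecutive samples are negative during the Post-Infusion Follow-Up period in Weeks 1-52 and/or Year 2".
- Section 12.8.3: "Sample testing during Years 2-5 is not required if at least 3 consecutive samples are negative during the Post-Infusion Follow-Up period in Weeks 1-52".
- Section 12.11: "Sample testing at the ETV is not required if at least 3 consecutive samples are below the limit of detection prior to the ETV".
- Section 12.9.2, for Years 6-7: "not required if at least 3 consecutive samples are below the limit of detection as of the end of Year 5".

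**Duty to continue.** Section 9.7.9.7 and Table 9.1.5 footnote e keep testing going after Week 52 only for subjects who have not had three consecutive negative semen samples by then.

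**The concern.** Each waiver from Week 33 through Year 5, and at early termination, asks whether a run of three negatives occurred at some time in a past period. It does not ask whether the subject is negative now. The Week 12 floor makes the difference matter. The protocol deliberately tests semen beyond an early negative run, yet gives no consequence if one of those extra samples is detectable.

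Vector shedding is a listed safety outcome. The sample condition for stopping contraception (inclusion criterion 6) is also met by any such run, and the donation advice in Section 9.6 lasts until there is no further evidence of shedding. Both rely on later semen results that, for this man, no waiver-governed visit has to supply.

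**Working it through.** The protocol states no figure on this point. The check applies the rules to one case, looks for a rule that rescues him, and counts the scheduled tests concerned.

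**1. The case.** Negative at Weeks 4, 6 and 8, detectable at Week 12. The run lies within Weeks 1-16, so it counts whether the Post-Infusion Follow-Up period means 16 weeks (Section 9.3.6) or Weeks 1-52 (Section 12.8.1). The Week 12 floor has been served. The waivers through Year 5 and at early termination are met.

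**2. Search for a rescuing rule.**
- *Week 52 continuation duty:* it covers men who have not had three consecutive negatives. He has had them.
- *Table 9.1.3 footnote e (Weeks 17-32):* collection runs until three consecutive negatives are obtained. It does not itself say that earlier negatives suffice, but Section 12.6.4, which covers Weeks 17-36, does.
- *Section 12.9.2:* the phrase about the end of Year 5 can be read as status at that date. Ambiguous.
- *Treatment failures on the abbreviated schedule* (Table 9.1.5 footnote h, Sections 9.7.9.7, 12.8 and 12.8.2): samples are due until shedding has cleared. This can be read as current status, so it may reach him if he is in that group.

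For the ordinary subject, nothing clearly restores a required test before Year 6.

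**3. How many result patterns are caught.** There are 7 samples before Week 12 (Days 2, 4, 8; Weeks 4, 6, 8, 10), hence 2^7 = 128 patterns ending in a detectable Week 12. Of these, 47 contain a run of three negatives and are waived. Using Weeks 4-10 only, it is 3 of 2^4 = 16. Under a rule based on the latest three samples, none is waived. These are counts of patterns, not probabilities.

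**4. Scheduled semen tests after Week 12 (nominal weeks).**
- Year 1: Weeks 14, 16, 20, 24, 28, 32, 36, 40, 44, 48, 52 = 11.
- Year 2: Weeks 56 to 104 every 4 weeks = 13.
- Years 3-5: (8 six-weekly + 1 End of Year) × 3 = 27.
- Years 6-7: Weeks 286, 312, 338, 364 = 4.
- Total: 11 + 13 + 27 + 4 = 55.

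**5. How many can still be regained.** The Amendment 9 summary says recruitment is complete. Being recruited is not the same as being dosed, so dosing by that date is an assumption.
- Amendment 9 (19 June 2020) to Amendment 10 (24 August 2021): 431 days / 7 = 61.6 weeks. Every subject is then past Week 61, and the Year 1 tests are gone. From Week 64 on: 11 + 27 + 4 = 42 at most.
- The Amendment 8 synopsis (31 January 2019) already describes FVIII levels in the second year of follow-up, so some men were past Week 52 then. To Amendment 10: 936 days / 7 = 133.7 weeks, and 52 + 133.7 = 185.7. What remains for them is Weeks 186, 192, 198, 204 and 208 (5), Year 5 (9) and Years 6-7 (4): 5 + 9 + 4 = 18 at most.

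These are upper bounds. Under the fix a man may stop after three clear samples. The last 4 tests in each count fall under the ambiguous Section 12.9.2.

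**The case against.** The best reply is that the protocol should be read as a whole. It speaks elsewhere of shedding being cleared, and a man whose last sample is detectable has not cleared it in any ordinary sense. The Week 12 floor, too, makes little sense unless the later result counts. This is fair as to what was probably intended, and for treatment failures on the abbreviated schedule it may secure further samples. It does not settle the matter for other subjects. The waivers name their own condition, and the continuation duty is tied to never having had three negatives.

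The reply also has force on consequences. The donation advice stays in force. Section 9.7.9.7 allows contraception to be extended on observed shedding and requires consultation between the Investigator and the Medical Monitor before it stops. Discretionary testing is not barred.

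A reader might infer more than the documents support:
- *That every such man is left without a required test.* The treatment-failure wording and Section 12.9.2 prevent so flat a statement.
- *That 55 tests are at stake.* That is the whole schedule after Week 12; the 11 in Year 1 cannot be regained in a fully recruited study.
- *That he may simply stop contraception.* The consultation requirement stands.
- *That the enrollment halt for persistent semen DNA (Section 9.3.4.1) is disabled.* With recruitment complete, nothing turns on this.
- *That reappearance has occurred.* No result reported in the documents shows it.

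**Conclusion.** The point stands as a minor defect in a stated stopping rule. Taken literally, the waivers release a man from required semen testing on a past run of three negatives even if a later required sample was detectable. Possible exceptions are treatment failures on the abbreviated schedule and Years 6-7.

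Assuming all subjects were dosed by Amendment 9, at most 42 scheduled tests per affected man remain, and at most 18 for men already past Week 52 at Amendment 8. The study has at most 15 subjects. The documents give no rate of reappearance after three negatives, so the number affected cannot be estimated and may be zero.

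**What to change.** Define semen clearance once: the three most recent consecutive samples are below the limit of detection, the last of them at or after Week 12, and any later detectable sample resets the count.

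Use that definition in Table 9.1.5 footnotes e and h, Sections 9.7.9.7, 12.8.1 to 12.8.3, 12.9.2 and 12.11, and inclusion criterion 6. For consistency, use it also in footnote e of Tables 9.1.2 to 9.1.4 and in Sections 12.5.4, 12.6.4 and 12.7.2.

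Add one transitional sentence: any subject already waived despite a later detectable semen sample is retested at his next scheduled visit, and at scheduled visits after that until the definition is met.

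The cost is one definition with cross-references and a few extra semen PCRs per affected man at visits already scheduled. A man whose last sample was the detectable one at Week 12 needs at least 3. Between Weeks 286 and 364 semen tests are 26 weeks apart, so three clear samples span 2 × 26 = 52 weeks; a man first retested at Week 338 could not complete them by Week 364 and would be reported as not shown to have cleared.
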